### Definition of baseline for efficacy analyses in non-randomized cohorts and for safety analyses

The last available assessment prior to the start of study treatment is defined as ‘baseline’ value or ‘baseline’ assessment for safety and efficacy (for non-randomized cohorts) analyses. If an assessment is planned to be performed prior to the first dose of study treatment in the protocol and the assessment is performed on the same day as the first dose of study treatment, it will be assumed that it was performed prior to study treatment administration, if assessment time point is not collected or is missing. If assessment time points are collected, the observed time point will be used to determine pre-dose on study day 1 for baseline calculation. Unscheduled assessments will be used in the determination of baseline. However, if time is missing, an unscheduled assessment on study day 1 will be considered to have been obtained after study treatment administration.

Patients who start treatment and discontinue from the study on the same day may have two different sets of data collected on study day 1 (one during study and one in the End of Treatment (EOT) visit). Data reported at the EOT visit are not eligible for baseline selection.

If a scheduled pre-dose measurement actually occurred post-dose, then the corresponding measurement will be treated and analyzed similar to an unscheduled post-dose measurement.

Baseline for RR and QT/QTc interval assessments will be derived from the visit where both RR and QT are not missing. Triplicate ECGs are collected in the study and the baseline for each ECG measurement is the average of the pre-dose replicate measurements on the baseline day. Unscheduled assessments will not be included in the calculation of the average. QTcB and QTcF will be derived based on RR and QT. The average of the replicate measurements will be determined after the derivation of the individual parameter at each time point.

### **3.4.2. Baseline characteristics**

Baseline characteristics (including demographics, disease history and prior anti-cancer therapies) are described in Section 6.5.1. These baseline characteristics are not planned to be included as stratification variables or covariates in statistical models unless otherwise specified in Section 6.

### **3.5. Safety Endpoints**

#### **3.5.1. Adverse events**

##### **Treatment-Emergent Adverse Events**

Treatment-emergent adverse events (TEAEs) are those events with onset dates occurring during the on-treatment period.

**On-treatment period** is defined as the time from the first dose of study treatment through minimum (30 days + last dose of study treatment, start day of new anti-cancer drug therapy – 1 day). The start day of new anti-cancer drug therapy after the first dose of study treatment is derived as outlined in Section 5.2.5.

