### **5.2.7. Definition of on-treatment period**

Safety endpoints will be summarized based on the on-treatment period unless otherwise specified.

On-treatment period is defined as the time from the first dose of study treatment through minimum (30 days + last dose of study treatment, start day of new anti-cancer drug therapy – 1 day).

Safety data collected outside the on-treatment period as described above will be listed and flagged in listings but not summarized.

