#### **6.6.1. Adverse events**

Treatment-emergent adverse events (TEAEs) are those events with onset dates occurring during the on-treatment period as defined in Section 3.5.1.

All analyses described will be based on TEAEs (started during the on-treatment period) if not otherwise specified. The AE listings will include all AEs (whether treatment-emergent or not). AEs outside the on-treatment period will be flagged in the listings.

- **Related Adverse Events:** adverse events with relationship to study treatment (as recorded on the AE eCRF page, Relationship with study treatment = Related) reported by the investigator and those of unknown relationship (ie, no answer to the question 'Relationship with study treatment'). Related AEs are those related to any study drug (ie, at least one of the study drugs).
- **Serious Adverse Events (SAE):** serious adverse events (as recorded on the AE eCRF page, Serious Adverse Event = Yes).
- **Adverse Events Leading to Interruption of Study Treatment:** adverse events leading to interruption of study treatment (as recorded on the AE eCRF page, Action taken with study treatment = Drug interrupted). The eCRF does not allow for a clear separation between interruption of an infusion and delays of administration for a parenteral drug as

both are recorded using the same term on the eCRF (“Drug interrupted”). IRRs will be excluded in the analysis of AEs leading to Drug Interruption in case they only led to an interruption of the infusion.

- **Adverse Events Leading to Permanent Treatment Discontinuation:** adverse events leading to permanent discontinuation of study treatment (as recorded on the AE eCRF page, Action taken with study treatment = Drug withdrawn).
- **Adverse Events Leading to Death:** adverse event leading to death (as recorded on the AE eCRF page, Outcome = Fatal, as well as AEs of Grade 5).
- **Immune-related Adverse Events (irAE):** irAEs (as identified according to the methodology outlined in Appendix 1 for a pre-specified search list of MedDRA PTs, documented in the Safety Review Plan (SRP) and finalized for analysis of the current study data prior to DB lock)
- **Infusion-related Reactions (IRR):** IRRs (as identified according to the methodology outlined in Appendix 2 for a pre-specified search list of MedDRA PTs documented in the SRP and finalized for analysis of the current study data prior to DB lock).

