#### 6.6.1.1. All adverse events

Adverse events will be summarized by worst severity (according to NCI-CTCAE version 4.03) per patient, using the latest version of MedDRA preferred term (PT) as event category and MedDRA primary system organ class (SOC) body term as Body System category.

In case a patient has events with missing and non-missing grades, the maximum of the non-missing grades will be displayed. No imputation of missing grades will be performed.

The following tables will be created:

- The overall summary of AEs table will include the frequency (number and percentage) of patients with each of the following by treatment group:
  - TEAEs
  - TEAEs, Grade  $\geq 3$
  - Related TEAEs
  - Related TEAEs, Grade  $\geq 3$
  - TEAEs leading to interruption of any study drug
  - TEAEs leading to discontinuation of avelumab

- TEAEs leading to discontinuation of utomilumab
- TEAEs leading to discontinuation of PF-04518600
- TEAEs leading to discontinuation of PD 0360324
- TEAEs leading to discontinuation of CMP-001
- TEAEs leading to discontinuation of any study drug
- Related TEAEs leading to discontinuation of avelumab
- Related TEAEs leading to discontinuation of utomilumab
- Related TEAEs leading to discontinuation of PF-04518600
- Related TEAEs leading to discontinuation of PD 0360324
- Related TEAEs leading to discontinuation of CMP-001
- Related TEAEs leading to discontinuation of any study drug
- Serious TEAEs
- Related Serious TEAEs
- TEAEs leading to death
- Related TEAEs leading to death
- irAEs
- IRRs
- Cytokine Release Syndrome (Combination F only)
- TEAEs by SOC and PT and worst grade
- TEAEs related to any study drug by SOC and PT and worst grade
- TEAEs leading to death by SOC and PT
- Related TEAEs leading to death by SOC and PT

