#### **6.6.1.3. Adverse events leading to discontinuation of study treatment**

The frequency (number and percentage) of patients with each of the following will be presented for TEAEs leading to permanent discontinuation of each study drug and study treatment, by treatment group:

- TEAEs leading to discontinuation of avelumab by SOC and PT
- TEAEs leading to discontinuation of utomilumab by SOC and PT
- TEAEs leading to discontinuation of PF-04518600 by SOC and PT
- TEAEs leading to discontinuation of PD 0360324 by SOC and PT
- TEAEs leading to discontinuation of CMP-001 by SOC and PT
- TEAEs leading to discontinuation of any study drug by SOC and PT
- Related TEAEs leading to discontinuation of avelumab by SOC and PT
- Related TEAEs leading to discontinuation of utomilumab by SOC and PT
- Related TEAEs leading to discontinuation of PF-04518600 by SOC and PT
- Related TEAEs leading to discontinuation of PD 0360324 by SOC and PT
- Related TEAEs leading to discontinuation of CMP-001 by SOC and PT
- Related TEAEs leading to discontinuation of any study drug by SOC and PT

The listing of all AEs leading to treatment discontinuation will also be provided with the relevant information.

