#### **Parameters with NCI-CTC grades available:**

The laboratory toxicities will be tabulated using descriptive statistics (number of patients and percentages) during the on-treatment period. The denominator to calculate percentages for each laboratory parameter is the number of patients evaluable for CTCAE grading (ie those patients for whom a Grade 0, 1, 2, 3 or 4 can be derived).

- The shift table will summarize baseline CTCAE grade versus the worst on-treatment CTCAE grade. The highest CTCAE grade during the on-treatment period is considered as the worst grade for the summary.
- The number and percentage of patients with newly occurring or worsening laboratory abnormalities during the on-treatment period will be summarized by worst grade on-treatment (Grade 1, 2, 3, 4, Grade 3/4 and any grade (Grades 1-4)).

The above analyses apply to hematology and chemistry evaluations which can be graded per CTCAE, ie:

- Hematology:  
Hemoglobin (HB), Leukocytes (white blood cell decreased), Lymphocytes (lymphocyte count increased/decreased), Neutrophils / Absolute Neutrophils Count (ANC) (neutrophil count decreased), Platelet Count (PLT) (platelet count decreased).
- Serum Chemistry:  
Albumin (hypoalbuminemia), Alkaline Phosphatase (alkaline phosphatase increased), Alanine Aminotransferase (ALT) (ALT increased), Amylase (serum amylase increased), Aspartate Aminotransferase (AST) (AST increased), Total Bilirubin (blood bilirubin increased), Creatinine (creatinine increased), Creatine Kinase (CPK increased), Potassium (hypokalemia/ hyperkalemia), Sodium (hyponatremia/ hypernatremia), Magnesium (hypomagnesemia/hypermagnesemia), Calcium (hypocalcemia/ hypercalcemia), Glucose (hypoglycemia/hyperglycemia), Gamma Glutamyl Transferase (GGT) (GGT increased), Lipase (lipase increased), Phosphates (hypophosphatemia).

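### TEAEs are defined by onset date alone, so an adverse event recorded before first dose that worsens on treatment under its original onset date is left out of the TEAE-based tables

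*SAP*

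**What the plan says.** Section 3.5.1 gives the definition: "Treatment-emergent adverse events (TEAEs) are those events with onset dates occurring during the on-treatment period". The on-treatment period "is defined as the time from the first dose of study treatment through minimum" of two dates: 30 days after the last dose, and the day before a new anti-cancer drug therapy starts. An onset before first dose is therefore outside it.

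Section 6.6.1 repeats the definition and sets its reach: "All analyses described will be based on TEAEs (started during the on-treatment period) if not otherwise specified". The AE listings hold every AE, and "AEs outside the on-treatment period will be flagged in the listings". Section 5.2.7 adds: "Safety data collected outside the on-treatment period as described above will be listed and flagged in listings but not summarized".

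The tables follow from this. Section 6.6.1.1 plans "TEAEs by SOC and PT and worst grade", Section 6.6.1.3 plans "TEAEs leading to discontinuation of any study drug by SOC and PT", and Section 6.6.3 limits the SAE tables to treatment-emergent SAEs.

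For gradable laboratory parameters, Section 6.6.5.1 takes another route: "The number and percentage of patients with newly occurring or worsening laboratory abnormalities during the on-treatment period" are summarized by worst on-treatment grade, next to a shift table from baseline grade.

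**The concern.** An AE record can open before first dose and still be active during treatment. If its grade rises after dosing, the clinically important part of the event lies inside the on-treatment period, but the onset date does not. The definition looks only at the onset date. The higher grade then reaches none of the TEAE-based summaries, even though it was observed on treatment.

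AE severity, seriousness and relationship are a secondary endpoint (Section 3.2.1), and immune-related events are AEs of special interest (Section 3.5.1). All combinations here add immune modulators to avelumab, so worsening of something already present is a question a safety reader will ask. Compared with a definition that counts worsening, the onset-only rule can lower a reported AE rate or leave it unchanged, but cannot raise it. Cohorts are small, so one patient is visible in the percentages.

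**Working it through.** The SAP gives no figure for this point, so there is none to reproduce. The check is to follow one case through the rules.

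**Case.** An AE record opens on study day -5 at Grade 1 and reaches Grade 3 on day 20. It stays one record with its day -5 onset.

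| Output | Condition in the SAP | Result |
|---|---|---|
| Overall, Grade 3 or higher, related, worst-grade and AE-leading-to-death tables (6.6.1.1) | TEAE | Left out |
| Interruption tables (6.6.1.2) | TEAE | Left out |
| Discontinuation tables (6.6.1.3) | TEAE | Left out |
| SAE tables (6.6.3) | Treatment-emergent | Left out |
| irAE tables (6.6.4; Appendix 1, Table 15 Step 2) | Onset at or after first study drug administration, up to 90 days after last dose, whatever the TEAE status | Fails the programmed step; medical review may add it |
| IRR tables (6.6.4; Appendix 2) | Onset on the day of infusion or the day after | Not met |
| DLT summary (3.1, 6.1.1.1; Phase 1b only) | AE that occurs in the DLT window, attributed to study drug and meeting the DLT criteria | May be counted |
| Deaths table (6.6.2) | All deaths in the safety analysis set | Counted if fatal |
| AE listings (6.6.1) | All AEs | Shown, flagged |

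**Laboratory counterpart.** A gradable parameter at Grade 1 at baseline and Grade 3 on day 20 is counted as worsened, under Grade 3 and under Grade 3/4, and appears in the shift table (6.6.5.1). ALT that goes from Grade 1 to Grade 3 is thus a Grade 3 laboratory case. The same course held as one continuing AE record with a pre-dose onset is in no TEAE table.

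**Size for one cohort.** Tables count patients, and each patient once per category. Let k be the number of affected patients with no other event in the category, and N the cohort's safety analysis set. The rate is lowered by 100 × k / N percentage points.

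- N = 20 (planned size of each Combination F cohort and several Combination A cohorts), k = 1: 100 × 1/20 = 5.0 points
- N = 12 (maximum at a dose level in Combinations B and D), k = 1: 100 × 1/12 = 8.3 points
- N = 6 (for example a Combination B dose level after 3 patients and 3 added), k = 1: 100 × 1/6 = 16.7 points
- N = 35 (planned size of Cohort A5), k = 1: 100 × 1/35 = 2.9 points

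The SAP does not give k. Assuming 0 to 2 such patients in a cohort of 20, the range is 0 to 100 × 2/20 = 10 points. A patient who already has another event in the category contributes 0. If each grade increase opens a new AE record, k = 0 throughout.

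**The case against.** The strongest objection is that the effect depends on a recording convention that is not visible. How grade changes are entered is commonly left to the protocol and CRF instructions, and a condition known at screening may sit in medical history (Section 6.5.1.2) and become a new AE when it worsens. In either case the event gets an on-treatment onset and is already a TEAE. This stands, and it makes the finding conditional. It does not remove it, because the SAP states no such convention and its definition, read literally, leaves the case out.

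It can also be said that the onset rule is deliberate and coherent. Sections 3.5.1 and 6.6.1 agree, and the version history records the change to onset dates. Laboratory values are repeated measurements with a baseline, so counting worsening is natural there. A reader might infer that the SAP contradicts itself, but it does not: these are two rules for two kinds of data. What remains is that the same clinical course is counted in one set of tables and not in the other, with no reason given.

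Three further inferences go too far.

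- *The worsened event disappears.* All AEs are listed, all deaths are tabulated, and a Phase 1b worsening can be a DLT. Liver tests also have their own on-treatment categories in Section 6.6.5.1.
- *An immune flare cannot become an irAE.* Appendix 1 lets medical review add cases that the algorithm misses, and the reviewed set is the basis of the irAE analyses.
- *Every affected patient costs 5, 8.3 or 16.7 points.* These are ceilings, reached only when the patient has no other event in the category.

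Finally, Section 5.3.2.2 moves a missing onset date, or a partial one in the month or year of first dose, to first dose. That can turn pre-dose events into TEAEs. It affects only incomplete dates and does nothing for a known pre-dose onset, but it means the one-way direction holds only in comparison with a definition that counts worsening.

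**Conclusion.** The point holds in a conditional form. For an AE recorded before first dose, kept under its original onset date, and then worse in grade or serious on treatment, the SAP as written gives no place in the TEAE-based tables and no programmed route to the irAE tables. The per-patient ceilings above apply only under that condition, and the number of such patients cannot be derived from the SAP. The conclusion rests on two assumptions: that worsening does not open a new record, and that the affected patient has no other event in the category. If either fails, the effect for that patient is nil. The gap is worth closing because the direction is known, the cohorts are small, and the correction does no harm if the convention already exists.

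**What to change.** In Sections 3.5.1 and 6.6.1, extend TEAEs to events with onset before first dose that increase in CTCAE grade or become serious during the on-treatment period, counted at the worst on-treatment grade. Make the matching change in Table 15 Step 2, using its own window of 90 days after last dose.

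If the AE page does not date grade changes within a record, use one of two fallbacks:

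- count a record with pre-dose onset that was ongoing at first dose and whose worst grade exceeds its pre-dose grade; or
- confirm in the SAP that each worsening is entered as a new record with its own onset date, in which case the present definition already captures it.

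The cost is a sentence in each place and a small change to the TEAE flag, provided the AE page holds the needed dates or a pre-dose grade; the SAP does not show whether it does. Reported AE rates may rise slightly.

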##### **Adverse Events of Special Interest (AESIs)**

AESIs are immune-related adverse events (irAE) and infusion-related reactions (IRRs). For Combination F, AESIs also include Cytokine Release Syndrome. The criteria for classification of an AE as an irAE or IRR are described in Appendix 1 and Appendix 2, respectively.

### **4. ANALYSIS SETS**

Data for all patients will be assessed to determine if patients meet the criteria for inclusion in each analysis population prior to releasing the database and classifications will be documented per Pfizer's standard operating procedures.

Only patients who signed informed consent will be included in the analysis sets below.

#### **4.1. Full Analysis Set**

For the randomized cohorts: The full analysis set (FAS) will include all randomized patients. Patients will be classified according to the study treatment assigned at randomization.

For non-randomized cohorts: The FAS will include all patients who receive at least one dose of study drug. Patients will be classified according to the study treatment actually received. If a patient receives more than one treatment the patient will be classified according to the first study treatment received.

#### **4.2. Safety Analysis Set**

For the randomized cohorts: The safety analysis set will include all patients who receive at least one dose of study drug. Patients will be classified according to the study treatment assigned at randomization unless the incorrect treatment(s) was/were received throughout the dosing period in which case patients will be classified according to the first study treatment received.

For non-randomized cohorts: The safety analysis set will include all patients who receive at least one dose of study drug. Patients will be classified according to the study treatment actually received. If a patient receives more than one study treatment, the patient will be

classified according to the first study treatment received. For the non-randomized cohorts, the FAS and the safety analysis set are identical.

### **4.3. Other Analysis Set**

#### **4.3.1. DLT-evaluable set**

This is the primary analysis set for the Phase 1 lead-in for all Combinations and includes all enrolled patients in Phase 1b who are eligible for the study, receive at least 1 dose of study treatment, and either experience DLT during the DLT observation period, or complete the DLT observation period.

- For Combinations A, B, C, and D, the DLT observation period is the first 2 cycles (8 weeks) of treatment.
- For Combination F, the DLT observation period will be 4 weeks including the first two weekly SC injections and the subsequent two weekly IT administrations.

Patients without DLTs who withdraw from study treatment before receiving at least 75% of the prescribed doses for all study drugs in the combination for reasons other than treatment-related toxicity (eg, missed appointments or development of rapidly progressing disease) are not evaluable for DLT.

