### Phase 1b lead-in

During Phase 1b, up to 18 NSCLC patients will be randomized 1:1:1 to 1 of 3 cohorts (6 patients each) to receive utomilumab at 500 mg (Cohort A1), 100 mg (Cohort A2), or 20 mg (Cohort A3) administered intravenously (IV) every 4 weeks (Q4W) in combination with 10 mg/kg of avelumab administered IV every 2 weeks (Q2W) for 2 cycles (ie, 8 weeks). If a dose-limiting toxicity (DLT) is observed in at least 2 of 6 DLT-evaluable patients treated within a cohort, further evaluation of the cohort will be stopped. Patients treated in Phase 1b who are not considered DLT evaluable (as defined in Section 3.1) will be replaced for the assessment of the DLT rate in the cohort to which they were randomized.

### Phase 2

For each utomilumab dose level that is tolerated (ie, not meeting the DLT criteria) in the Phase 1b lead-in, the corresponding dose level cohort(s) will continue enrollment for Phase 2 with up to 22 additional patients each. Therefore, all 3 cohorts could potentially enroll additional patients.

In addition to potential expansion of enrollment of patients with NSCLC to Cohorts A1, A2, or A3, Phase 2 will also enroll patients with melanoma (Cohort A4; N=28), SCCHN (Cohort A5; N=35), TNBC (Cohort A6; N=20), SCLC (Cohort A7; N=20), and first-line advanced NSCLC (Cohort A8; N=20, up to 26 patients will be enrolled to achieve a minimum of 20 PD-L1-positive patients). Enrollment into Cohorts A7 and A8 may be staged based on activity observed during the Phase 1b part of the combination (ie, new cohorts may be opened based on activity data emerging from the randomized dose level cohorts of Combination A).

For Cohorts A4 through A8, the projected utomilumab dose to be used in each of these cohorts is 100 mg which may be modified based upon emerging safety data for utomilumab from randomized dose cohorts of Combination A. In the event that the utomilumab dose is modified after the initiation of Cohorts A4 through A8, additional patients will be enrolled to achieve the target number of patients treated at the modified dose.

Sequenced (single agent administration for 1 cycle followed by combination therapy) administration of single agent avelumab or utomilumab for 1 cycle followed by administration of combination (avelumab plus utomilumab) will be evaluated in 2 additional cohorts. Both cohorts will enroll 20 patients each with PD-L1 positive, 1L advanced NSCLC. Cohort A9

[figure not shown]

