**Important for Combination F:** CMP-001 activates pDCs through agonism of TLR9. Upon activation by CMP-001, pDCs will induce large amounts of IFN $\alpha$  and Th1-promoting cytokines. Therefore, it is expected that toxicities associated with CMP-001 dosing may resemble interferon-related toxicities and symptoms associated with cytokine release, such as fever, flu-like symptoms, tachypnea, headache, tachycardia, hypotension, rash, and hypoxia which may present hours after CMP-001 injection. Therefore, AEs such as headache, fever, flu-like symptoms and/or hypotension that are  $\leq$  Grade 3 AND resolved to  $\leq$  Grade 1 within 24 hours with standard supportive care will not be considered as DLTs.

- Non-hematologic Grade  $\geq 3$  laboratory abnormality if medical intervention is required to treat the patient or the abnormality leads to hospitalization.
  - Single laboratory values out of normal range that are unlikely related to trial treatment according to the Investigator, do not have any clinical correlate, and resolve to Grade  $\leq 1$  within 7 days with adequate medical management are not to be considered DLTs;
  - ALT or AST  $> 3$  x upper limit of normal (ULN) (if normal at baseline) or  $> 3$  x ULN and doubling the baseline (if  $> ULN$  at baseline) associated with bilirubin  $> 2$  x ULN.

Non-Adherence to Treatment Schedule:

- Delay of  $\geq 3$  weeks in receiving the next scheduled administration due to persisting treatment-related toxicities;
- Failure to receive at least 75% of the planned doses each of the investigational products during the DLT observation period due to treatment-related toxicities.

In the absence of associated clinical abnormalities, abnormal laboratory tests should be repeated to confirm relevance.

While the rules for adjudicating DLTs in the context of the dose determination phase (Phase 1b) are specified above, an AE not listed above, or an AE meeting the DLT criteria above but occurring outside of the DLT observation period may be defined as a DLT after consultation between Sponsor and Investigator, based on the emerging safety profile.

- Phase 2: Confirmed objective response (OR), as assessed by the Investigator using RECIST v1.1.

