##### Phase 1b lead-in

There is no formal hypothesis testing in this phase. However, before expanding NSCLC Cohorts A1, A2, and/or A3 after the lead-in phase, the safety must be confirmed in the first 6 patients evaluable for DLT in those treatment groups. The dose level is considered as safe and a treatment group can be expanded when there are not more than 1 of 6 patients with DLTs within the first 2 cycles of treatment.

##### Phase 2

Hypotheses will be tested separately for each treatment group based on OR rate (ORR, proportion of patients with OR) using the data from the combined Phases 1b and 2 (Cohorts A1, A2, A3) and the data from Phase 2 (Cohorts A4, A5). There is no formal hypothesis testing for Cohorts A6, A7, A8, A9, and A10. These cohorts use an estimation approach.

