### 5.1.2. Decision rules

#### Combination A

#### Phase 1b lead-in

Table 7 shows the probability of confirming the safety in the first 6 patients for a range of underlying true DLT rates. For example, for a DLT that occurs in 10% of patients, there is a greater than 89% probability of confirming safety and expanding the corresponding treatment group. Conversely, for a DLT that occurs with a rate of 60%, the probability of expanding is 4%.

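### The 75%-of-doses exclusion from the DLT-evaluable set applies only to patients who withdraw, so a patient under-dosed for non-toxicity reasons who stays on treatment counts as evaluable without a DLT

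*SAP*

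**What the plan says.** SAP Section 4.3.1 defines the primary analysis set for the Phase 1b lead-in of every combination. An eligible Phase 1b patient enters it if they "receive at least 1 dose of study treatment" and "either experience DLT during the DLT observation period, or complete the DLT observation period". One exclusion follows: "Patients without DLTs who withdraw from study treatment before receiving at least 75% of the prescribed doses for all study drugs in the combination" and who do so "for reasons other than treatment-related toxicity (eg, missed appointments or development of rapidly progressing disease) are not evaluable for DLT".

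Section 3.1 lists among the DLTs: "Failure to receive at least 75% of the planned doses each of the investigational products during the DLT observation period due to treatment-related toxicities". That criterion does not depend on withdrawal.

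For Combination A, Section 2.2.1 says that Phase 1b patients "who are not considered DLT evaluable (as defined in Section 3.1) will be replaced". Under Section 5.1.1, "a treatment group can be expanded when there are not more than 1 of 6 patients with DLTs". For Combination F, Section 5.1.1 expands a cohort with at most 1 DLT in 6. With 2 in 6 it adds up to 6 evaluable patients and expands with at most 3 in 12. For Combinations B, C and D, Section 5.1.2 lets Phase 2 start with at most 3 DLTs in 12 evaluable patients (10 for Combination C). Section 6.1.1.1 summarises DLTs on this set.

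**The concern.** The inclusion sentence asks for one dose and completion of the period. The exclusion removes under-exposed patients only if they withdraw from study treatment. A patient who skips doses for a reason unrelated to toxicity, does not withdraw and reaches the end of the period passes the first test and is not caught by the second. That patient is not replaced and is counted as having no DLT.

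Missed appointments are the plan's own example of a non-toxicity reason, yet they often cost a patient doses without any withdrawal. Nothing else in the SAP closes the gap.

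The Phase 1b rules work on 6 to 12 patients. Tables 7 and 8 describe those rules as if every counted patient carried the full DLT risk. If some counted patients carry less, the reported DLT rate is too low and the rules are more permissive than the tables say.

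**Working it through.** **Step 1. Can a patient complete the period while under-dosed?** For Combinations A to D the period is the first 2 cycles (8 weeks). Section 6.5.3 derives a cycle start date even when every study drug had dose zero at the Day 1 visit, so cycles can run with doses omitted. For Combination F, Section 4.3.1 describes the 4-week period as including the first four CMP-001 administrations. Completing it may therefore imply that CMP-001 was given. It implies nothing about avelumab, utomilumab or PF-04518600.

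**Step 2. How many missed doses cross 75%?** Schedules are from Sections 2.2 and 3.4.1.
- Utomilumab Q4W over 8 weeks (A, D): 2 doses. One missed leaves 1/2 = 50%.
- Any Q2W drug over 8 weeks (A to D): 4 doses. One missed leaves 3/4 = 75%, which still meets the criterion; two missed leave 50%.
- Avelumab Q2W over 4 weeks (F): 2 doses. One missed leaves 50%.

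**Step 3. Reproduce the plan's tables.** With p the true DLT rate:
- Combination A: P(expand) = (1-p)^6 + 6p(1-p)^5. At p = 0.3 this is 0.1176 + 0.3025 = 0.420. Rates of 10% to 70% give 0.886, 0.655, 0.420, 0.233, 0.109, 0.041, 0.011, which agree with Table 7 after rounding. (The text of Section 5.1.2 says "for a DLT that occurs in 10% of patients, there is a greater than 89% probability of confirming safety"; the exact value is 88.6%.)
- Combination F: P(at most 1 in 6) + P(2 in 6) × P(at most 1 in the next 6). At p = 0.3 this is 0.4202 + 0.3241 × 0.4202 = 0.556; Table 8 gives 0.56.

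**Step 4. Put one under-dosed patient among the first six.** The number of such patients and their risk are assumptions, since the SAP gives neither. I take the risk as between half the full risk (0.15 at p = 0.3) and zero. For five fully dosed patients at p = 0.3: P(0) = 0.1681, P(1) = 0.3602, P(2) = 0.3087, so P(at most 1) = 0.5282.
- Combination A, zero risk: 0.528.
- Combination A, half risk: 0.85 × 0.5282 + 0.15 × 0.1681 = 0.474.
- Combination F, zero risk: 0.5282 + 0.3087 × 0.4202 = 0.658.
- Combination F, half risk: P(2) = 0.85 × 0.3087 + 0.15 × 0.3602 = 0.3164, so 0.4742 + 0.3164 × 0.4202 = 0.607.

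| Rule and true DLT rate | All fully dosed | One of first six, half to zero risk |
|---|---|---|
| Combination A, 30% | 0.42 | 0.47 to 0.53 |
| Combination A, 40% | 0.23 | 0.29 to 0.34 |
| Combination F, 30% | 0.56 | 0.61 to 0.66 |

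With two such patients in six, the Combination A figure at 30% becomes 0.53 to 0.65. For the rule of at most 3 in 12 (B and D), taken alone at a true rate of 33%, the probability of passing rises from 0.40 to 0.48 if one of the twelve carries no risk.

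**Step 5. Could one such patient have changed the Combination A decision?** Section 2.2.4 reports Combination A's Phase 1b complete with no DLTs. If one of a cohort's six were replaced and the replacement had a DLT, the count would be 1 of 6, which still meets the rule.

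**The case against.** Several points on the other side have force.

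- **Intent.** Citing missed appointments suggests that the authors meant under-dosing for non-toxicity reasons to make a patient non-evaluable. That is plausible, but programming follows the text, and the text requires withdrawal.
- **Risk.** A patient with all four avelumab doses and one of two utomilumab doses is not unexposed. This stands. Zero risk is an outer bound, and at half risk the effect is about half as large.
- **Combination F.** The CMP-001 injections are named as part of the period, so the gap is at least partly closed for that drug. This stands, and the Combination F figures apply mainly to the other drugs.
- **Timing.** Phase 1b of Combinations A and B is reported complete, and Combination C did not go beyond Phase 1b, for lack of activity. SAP version 6 places the primary analysis after last subject last visit. For these combinations new wording can change the reported denominator, not enrolment.
- **Link to the protocol.** The SAP's version history ties this definition to protocol amendments. The protocol is not shown and may word the rule differently.

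A reader might infer that a toxic dose was wrongly declared safe, or that patients under-dosed because of toxicity are counted as free of DLT. The document supports neither. It does not show that any such patient existed, Step 5 rules out an effect of one such patient per cohort in Combination A, and Section 3.1 makes toxicity-driven under-dosing a DLT.

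**Conclusion.** The point holds, confined to under-dosing for reasons other than treatment-related toxicity in patients who stay on treatment. For them Section 4.3.1 gives the wrong denominator and is out of step with Section 3.1.

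The direction of the error rests on one assumption: that an under-dosed patient has a lower DLT risk than a fully dosed one. The size depends on how many such patients there were and on their risk, both unknown, so the ranges in Step 4 are illustrations and not estimates of what happened. One such patient in six adds 5 to 11 percentage points to the Combination A probability of expanding at a true rate of 30%, and 5 to 10 points under the Combination F rule.

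For Combination A the consequence is for the reported DLT denominator and for the claim that six adequately exposed patients supported each dose level. It is not for a decision that one such patient could have changed. This is worth correcting before the analysis sets are finalised; it does not show that any safety conclusion is wrong.

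**What to change.** In Section 4.3.1, define as not evaluable any patient without a DLT who, during the DLT observation period, receives less than 75% of the prescribed doses of any one study drug in the combination for reasons other than treatment-related toxicity, whether or not the patient withdraws.

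The per-drug wording matters. The present reference to all study drugs can be read as under 75% on every drug, and would then miss a patient with full avelumab and half the utomilumab.

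Reconcile the new text with the 75% criterion in Section 3.1, with the protocol definition, and with Section 2.2.1, which points to Section 3.1 for evaluability although the definition is in Section 4.3.1. Report the DLT summary on the revised set and state how many patients the change removes, by cohort.

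The cost is a sentence in the SAP, a check of dosing records for Phase 1b patients, and alignment with the protocol. Section 2 of the SAP says that major changes to the primary endpoint's definition or analysis are also reflected in a protocol amendment, so the sponsor should decide whether this counts as one. A few patients may leave the DLT denominator, and some cohorts could then show fewer than six evaluable patients. If there were no such patients, no result changes.
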